### **3. Data Collection**

The EMR will be reviewed to collect preoperative, intraoperative, and POD 0 data points. We will use the following method to identify the occurrence of a procedure-related adverse event: The EMR will be reviewed for patient phone calls for a procedure-related complication, unscheduled office visits, emergency department visits, hospital readmissions or reoperations within 30 days, and adverse events occurring up to 6 weeks post-operatively. The adverse events of interest will include the following:

- Wound infection
- Hematoma
- Transfusion
- Pelvic abscess
- Osteomyelitis
- Venous thromboembolism (deep vein thrombosis or pulmonary embolism)
- Delayed bowel or urinary tract injury
- Bowel obstruction or ileus
- Cardiac or pulmonary complication
- Neurologic injury

We will also employ an approach that will allow us to capture events that may have been handled outside of the CCHS or in institutions that do not utilize *Epic*. To capture these data points if they exist, we will contact participants by telephone on POD 1 (within 24 hours of surgical completion time) to determine if they received any care from a facility outside of the CCHS and then again at the post-operative follow up visit, which generally occurs at 6 weeks. We will then use these data with the Clavien Dindo Scale to determine the severity of the adverse event, with a grade 3 or higher considered to be a serious adverse event, and we will compare this proportion to the reference proportion of 26.3%. A proportion of patients with grade 3 or higher less than 45.1% will be considered non-inferior to the reference.

As part of the effort to characterize the patient population, we will extract data regarding total procedure-related costs using the EMR. We will assess satisfaction using the quality of recovery questionnaire, visual analog scores for postoperative pain, and a patient satisfaction survey described by Fountain et al at the postoperative visit, which uses a Press Ganey scale for responses (See Appendix A). Please see data collection sheet for a comprehensive list of planned data points.

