### **Specific Aims**

**Aim 1.** To compare the incidence of adverse events in patients following a SDD protocol for minimally invasive sacrocolpopexy compared to those patients discharged on POD 1.

We hypothesize that there is no difference in the incidence of adverse events between SDD compared to discharge on POD 1 after minimally invasive sacrocolpopexy. Using the *Epic* electronic medical record (**EMR**), we will evaluate 1) the number of unscheduled office visits, patient-initiated calls for a surgery-related complication, emergency department visits, and readmissions/reoperations of patients who had a SDD protocol and 2) the severity of any adverse events using the Clavien Dindo Scale. We will utilize patient phone calls to inquire about any of the aforementioned events outside of our institution. We will compare incidence of postoperative adverse events between patients undergoing SDD versus a historical control group who were discharged on POD 1.

**Aim 2.** To compare the total procedure-related costs associated with SDD compared to discharge on POD 1 for minimally invasive sacrocolpopexy.

We hypothesize that the total costs associated with SDD following minimally invasive sacrocolpopexy is less than the same procedure with discharge on POD 1. We will utilize data from the billing function of *Epic* EMR to compare total procedure-related costs for each approach to minimally invasive sacrocolpopexy.

**Aim 3.** To determine patient satisfaction with SDD after minimally invasive sacrocolpopexy.

We hypothesize that patients will be satisfied with SDD after minimally invasive sacrocolpopexy. We plan to address this aim using a series of validated measures.

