### **4. Statistical Plan**

*Statistical analysis:* Categorical variables will be presented as n/N (%) with 95% confidence intervals. Continuous variables will be presented as mean +/-SD or median [range]. A Pearson's chi-square test or Fisher exact test will be used for frequencies and proportions of categorical values and t test or the non-parametric Wilcoxon rank sum test for mean values of continuously measured variables. P values  $\leq 0.05$  will be considered statistically significant and we will use SAS (version 9.4, The SAS Institute, Cary NC) as our statistical package to perform these analyses. The primary investigator will perform the statistical analysis with assistance from the WHI statistician.

We will use data from a historical control group discharged on POD 1 after minimally invasive sacrocolpopexy to examine Aim 1 and Aim 2. This is a cohort of 60 women matching our eligibility criteria from a prospective randomized trial of two different types of lightweight polypropylene mesh (IRB #14-354). This study completed recruitment 2017. It consists of a group of women who underwent minimally invasive sacrocolpopexy using the same surgical approaches, at the same institutions (main campus, Fairview and Hillcrest), and performed by the same surgeons as our study. The primary difference is that participants in that study and the cohort proposed here is that all participants were discharged home on POD 1. We will utilize this cohort to compare the incidence and severity of procedure-related adverse events and costs between SDD and POD 1. Comparisons on outcome measures will be done using either an ANOVA analysis or a student's t test for parametric continuous outcomes, a Kruskal-Wallis or Mann Whitney U test for non-parametric outcomes and a Chi-square test for all categorical outcomes. Logistic regression will be performed to control for confounding variables.

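### Aim 1 compares patients who are asked about care outside the health system with historical controls whose capture of such care is not described, so equal ascertainment cannot be assumed

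*Combined protocol and SAP*

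**What the plan says.** Section 3 (Data Collection) gives two sources of events for SDD patients. The first is EMR review. The second is a direct enquiry about care elsewhere, made by telephone on POD 1 "to determine if they received any care from a facility outside of the CCHS". The same question is put a second time at the routine visit, about 6 weeks after surgery. Specific Aims, Aim 1, describes the same addition: "We will utilize patient phone calls to inquire about any of the aforementioned events outside of our institution". The answers are then graded: "We will then use these data with the Clavien Dindo Scale to determine the severity of the adverse event".

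Aim 1 sets the result against an earlier cohort: "We will compare incidence of postoperative adverse events between patients undergoing SDD versus a historical control group who were discharged on POD 1". Section 4 (Statistical Plan) identifies that cohort: "This is a cohort of 60 women matching our eligibility criteria from a prospective randomized trial of two different types of lightweight polypropylene mesh". It adds that the mesh trial completed recruitment in 2017, names day of discharge as the main difference between the cohorts, and uses these women to compare both incidence and severity of adverse events. Section 1 (Study Design) calls the control data prospectively collected. No section says how control events were found, whether control patients were asked about outside care, or over what period.

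**The concern.** The outside-care enquiry exists because EMR review alone can miss events treated elsewhere. If one cohort has that enquiry and the other does not, the first shows more events at the same true rate. Aim 1 is the study's only direct two-group safety comparison, and its hypothesis is that there is no difference. Emergency visits and readmissions, which may occur at other hospitals, are exposed in the same way as graded adverse events.

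The only adjustment planned is logistic regression for confounders that are not named. Regression on patient characteristics cannot repair a difference in how the outcome itself was ascertained. At the stakes here, with few serious events expected in either cohort, a difference of one or two captured events is a visible part of the total.

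**Working it through.** **1. The plan's own figure, to fix the scope.** Section 4 gives 45 patients, a reference of 26.3%, a one-sided exact test, 80% power and a detectable proportion of 45.1%. With alpha 0.05, the smallest r with P(X ≥ r | 45, 0.263) ≤ 0.05 is r = 18 (actual size 0.031). P(X ≥ 18 | 45, 0.451) = 0.798, and 80% is reached at 45.15%, so the stated figure reproduces. No quantity from the 60 controls enters it. How control events were captured therefore cannot move this criterion.

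**2. The two cohorts side by side.**

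| | SDD cohort | Historical controls |
|---|---|---|
| EMR review | Yes (section 3) | Not stated |
| Outside-care question, POD 1 | Yes (section 3) | Not stated |
| Outside-care question, about 6 weeks | Yes (section 3) | Not stated |
| Window | 30 days for readmission or reoperation, up to 6 weeks for adverse events | Not stated |

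The POD 1 question matters least. It covers the first 24 hours, when women discharged on POD 1 were in hospital or just leaving and had little chance of outside care. The 6-week question is the main possible asymmetry.

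**3. Size of the shift (illustration).** Inputs from section 4: true rate 12% in both cohorts (the planners' expected incidence), 45 SDD patients, 60 controls. Assumed, because the documents give no figure: a share m of control events missed, with SDD capture complete.

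- Expected events: SDD 45 × 0.12 = 5.4; controls 60 × 0.12 = 7.2.
- Observed control rate = 0.12 × (1 − m). False excess for SDD = 0.12 × m. Control events missed = 7.2 × m.

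| m | Observed control rate | False excess | Control events missed | Chance of wrongly finding SDD worse |
|---|---|---|---|---|
| 0 | 12.0% | 0 | 0 | 2.9% |
| 10% | 10.8% | 1.2 points | 0.7 | 4.3% |
| 20% | 9.6% | 2.4 points | 1.4 | 6.4% |
| 30% | 8.4% | 3.6 points | 2.2 | 9.3% |

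The last column enumerates all outcomes of an uncorrected Pearson chi-square test at two-sided 0.05, 45 against 60, counting only rejections in which SDD looks worse.

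**4. Sensitivity to the true rate.** At 26.3% in both cohorts, m of 10% to 30% gives a false excess of 2.6 to 7.9 points, and the chance of wrongly finding SDD worse rises from 3.0% to between 5.9% and 18.9%. At 5.4%, the lower published rate in section 4, the excess is 0.5 to 1.6 points and the chance rises from 3.0% to between 4.0% and 6.9%.

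**5. Scale against sampling error.** At 12%, the standard error of the difference is √[0.12 × 0.88 × (1/45 + 1/60)] = 0.064, or 6.4 points. The shift of 1.2 to 3.6 points is 0.2 to 0.6 standard errors.

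**The case against.** The strongest reply is that silence about another trial's methods is not evidence that they differed. The controls come from a prospective randomized trial at the same institutions with the same surgeons, and that trial may have asked about outside care at its own visits. This stands: the documents do not show a difference in capture, only that none can be ruled out.

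It can also be said that section 3 sends the graded data to the fixed 26.3%, and section 4 does not say which sources enter the two-group comparison. That is correct. But Aim 1 places the outside-care enquiry directly before the comparison with controls, and no text restricts the comparison to EMR events, so the combined count is the natural reading.

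Third, the shift is modest against sampling error, and it runs against SDD, so it would not falsely support SDD as safe. Both points stand. They limit the seriousness, but a spurious excess would still misinform a study meant to support wide adoption.

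Finally, an EMR-only comparison has its own bias. Controls spent their first night as inpatients and were fully observed, while SDD patients were at home. Dropping outside care they reported would remove real SDD events and could favour SDD. This stands too, and is why an EMR-only analysis should not simply replace the all-source one.

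**Conclusion.** The point holds as a gap in the Aim 1 two-group comparison. Outside care is actively sought in the SDD cohort, its capture in the controls is undescribed, and nothing in the plan aligns the two. Under-capture in controls would make SDD look worse. With an assumed 10% to 30% of control events missed at a true 12%, the false excess is 1.2 to 3.6 points, or 0.7 to 2.2 of 7.2 expected control events. It is nil if capture matched. The missed share is an assumption, and SDD capture is taken as complete.

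Three stronger readings go beyond the documents:

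- A reader might infer that the comparison does mix two capture methods. That requires knowing the control trial's method, which is not given.
- A reader might infer that the control trial is over and its patients can no longer be asked. The text says only that recruitment was completed; the end of follow-up is not stated.
- A reader might infer that the primary non-inferiority conclusion is biased. That criterion is one-sample against a fixed 26.3% with a 45.1% threshold and does not use these controls.

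This is a cheap improvement to make, not a flaw that invalidates the design.

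**What to change.** 1. Record for each SDD event whether it was found by EMR review or by patient enquiry only.
2. Establish from the mesh trial's protocol and data how, and over what window, it captured outside care, and state this in section 4.
3. If capture matched, compare all events.
4. If it differed or cannot be established, report the two-group comparison on events found by the same EMR review, event list, grading and window in both cohorts, side by side with the all-source comparison. State that EMR-only capture may miss true SDD events.
5. Keep all sources for the one-sample primary proportion.

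The cost is one source flag per event, easiest to set during data collection, a check of the control trial's methods, and one extra analysis. No change to sample size or patient contact is needed.

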### Inclusion Criteria:

Preoperative requirements include:

- Age <80 years old
- Preoperative American Society of Anesthesiologists grade I (normal healthy patient) or II (mild systemic disease)
- Access to ancillary care, including phone advice, nurse and outpatient clinic numbers
- Caretaker at home for at least 24 hours post-operatively
- Able to speak and read English
- Has decision-making capacity and able to provide consent for research participation

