*Sample size:* We estimate that approximately 80 minimally invasive sacrocolpopexy surgeries will be performed per year. Of these, we anticipate that ~3/4 will meet eligibility criteria and of these patients, ~3/4 will consent to participate. Based upon data by Unger et al, a Clavien Dindo grade 3 adverse event (defined as requiring surgical, endoscopic, or radiologic imaging/intervention) was identified in 26.3% of patients after a minimally invasive sacrocolpopexy. A meta-analysis of laparoscopic versus open sacrocolpopexy combined results of 9 randomized control-trials and found a post-operative complication rate of 5.4% after minimally invasive sacrocolpopexy (robotic and laparoscopic). We suspect that 26.3% may be an overestimation of adverse events as the Unger et al study included any imaging required in the postoperative period even if the result was normal. However, we also suspect that a 5.4% adverse event incidence may be low. As such, we feel that an adverse event incidence of 12% may be more representative of that expected after this surgical procedure.

We used a one-sided exact test for non-inferiority of binomial proportion to determine the degree of difference between the proportion of 26.3% and an incidence proportion greater than the reference which could be detected and deemed inferior (significantly greater) to the reference with a power of 80%. With a sample size of 45 patients, the proportion of patients with a Clavien Dindo grade of 3 will need to be 45.1% or greater. We will account for a 3% drop out rate (based on 2016 post-operative visit "no-show" rates for the Urogynecology division) by recruiting an additional 2 patients, making the sample size planned for this study a total of 47 patients.

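### The only stated non-inferiority criterion rests on a 26.3% reference that the protocol itself suspects is too high, while the 12% it prefers enters no calculation or rule

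*Combined protocol and SAP*

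**What the plan says.** Section 3 (Data Collection) grades adverse events on the Clavien Dindo scale, treats grade 3 or higher as serious, and states: "we will compare this proportion to the reference proportion of 26.3" per cent. The decision rule follows: "A proportion of patients with grade 3 or higher less than 45.1% will be considered non-inferior to the reference".

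The sample-size paragraphs of section 4 (Statistical Plan) take the 26.3% from a published series and then question it: "We suspect that 26.3% may be an overestimation of adverse events". The reason given is that the series "included any imaging required in the postoperative period even if the result was normal". A meta-analysis that "found a post-operative complication rate of 5.4% after minimally invasive sacrocolpopexy" is judged possibly too low. The authors settle in between: "we feel that an adverse event incidence of 12% may be more representative of that expected after this surgical procedure".

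The next paragraph returns to 26.3%. It uses a "one-sided exact test for non-inferiority of binomial proportion" with 45 patients and 80% power and arrives at 45.1%. The 12% does not appear again.

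Section 4 also plans to compare adverse events with 60 women from an earlier trial, all discharged on postoperative day 1 (POD 1), by chi-square test, with logistic regression for confounding. It gives no margin, power or safety criterion for that comparison.

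**The concern.** Aim 1 asks whether SDD is as safe as discharge on POD 1. The authors give their best judgement of the serious-event rate after this operation, explain why a published figure of more than twice that size may be too high, and then build the only explicit safety criterion on the larger figure without saying why.

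If 12% is about right, a cohort with twice the expected number of serious events would still lie below the 26.3% reference before any allowance is added. The allowance then raises the passing limit to 45.1%. A favourable result would be reported as non-inferior safety, in a study meant to support wide adoption of SDD, although the rule could hardly have produced any other answer.

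**Working it through.** **Inputs.** From section 4: reference 26.3%, preferred rate 12%, 45 evaluable patients, 80% power, one-sided exact binomial test, 60 historical controls. From section 3: non-inferior if the observed proportion is below 45.1%. The alpha of the one-sided test is not given separately. I assume 0.05, the plan's general significance level.

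**1. Reproducing the plan's figure.** Let X be the number of patients out of 45 with a grade 3 or higher event. Find the smallest c with P(X ≥ c | p0) ≤ 0.05, then the p1 at which P(X ≥ c | p1) = 0.80.

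- p0 = 0.263: P(X ≥ 17) = 0.061 and P(X ≥ 18) = 0.031, so c = 18 (40%).
- P(X ≥ 18 | p1) = 0.80 gives p1 = 0.4515. Power at 0.451 is 0.798.

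The stated 45.1% is therefore reproduced. With alpha 0.025 the result would be 47.4%, which does not match, so 0.05 is the likely setting.

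**2. What the stated rule does.** 0.451 × 45 = 20.3, so at most 20 events (20/45 = 44.4%) counts as non-inferior.

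| True SDD rate | Multiple of 12% | P(X ≤ 20), declared non-inferior |
|---|---|---|
| 12% | 1 | >0.999 |
| 24% | 2 | 0.999 |
| 26.3% | 2.19 | 0.997 |
| 36% | 3 | 0.908 |
| 45.1% | 3.76 | 0.526 |

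**3. The same test with 12% as reference.**

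- p0 = 0.12: P(X ≥ 9) = 0.084 and P(X ≥ 10) = 0.038, so c = 10 (22.2%), with actual size 0.038.
- P(X ≥ 10 | p1) = 0.80 gives p1 = 0.267.
- P(X ≥ 10) is 0.67 at a true rate of 24% and 0.98 at 36%.
- If SDD truly runs at 12%, it is left unflagged with probability 1 − 0.038 = 0.962.

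**4. The historical comparison as a safeguard.** For 12% of 60 against 24% of 45, two-sided 0.05, power is about 37% by the normal approximation and about 41% when the chi-square test (no continuity correction) is evaluated over all possible tables. A true doubling would be missed more often than found.

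**5. What a pass at 12% would mean.** With 9/45 (20.0%) the test does not flag SDD, yet the exact one-sided 95% upper limit is 32%. Failing to exceed 12% is not evidence of non-inferiority to 12%.

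**The case against.** The strongest reply has five parts.

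- **Aim 1 has a direct comparator.** A reader might infer that safety is judged only against 26.3%. It is not: section 4 also compares SDD with 60 women described as meeting the same eligibility criteria, from the same institutions and surgeons. This stands as a limit on the point. But that comparison has no criterion attached and low power, so it does not replace the rule in section 3.
- **The 12% is soft.** A reader might infer that the protocol establishes that 26.3% is inflated, or that POD 1 care gives 12%. The wording is hedged, no source is cited for 12%, it is called an adverse event incidence without a grade, and it refers to the operation, not to a discharge policy. This stands too. It is still offered directly as the alternative to the 26.3% grade 3 rate, and the plan gives no reason for setting it aside.
- **The endpoint may count imaging.** It is tempting to say that a normal scan is not an event in this trial. Section 3 lists complications, which leans that way, but does not say so, and section 4 describes grade 3 in terms that include imaging. If imaging counts, 26.3% is closer to like for like, and a 12% reference would flag SDD with probability 0.78 at a true rate of 26.3%. The definition must therefore be settled together with the reference.
- **Low-risk selection is not proven.** Eligibility requires "Preoperative American Society of Anesthesiologists grade I (normal healthy patient) or II (mild systemic disease") and age under 80, which suggests lower risk, but the case mix behind 26.3% is not described. The limit on start time is linked only to the chance of SDD, not to adverse events. The point does not rest on selection.
- **An 18/45 cut-off is not in the plan.** It is implied by the sample-size calculation only. The probabilities that matter are therefore those for the stated rule of at most 20/45.

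**Conclusion.** The point holds in this form: the only stated non-inferiority criterion is derived from a reference that the authors suspect is too high, and the rate they prefer is not used. If the expected rate is about 12%, the rule passes a doubled rate with probability 0.999 and a tripled rate with probability 0.91, so a pass says almost nothing about whether safety is preserved.

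These probabilities depend on 45 evaluable patients and on reading 12% as the expected grade 3 or higher rate. They do not depend on alpha, because the rule in section 3 is a plain cut-off on the observed proportion. The 10/45 threshold does assume one-sided 0.05.

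The documents do not show that the true rate is 12%, nor that normal imaging is excluded from this trial's endpoint. The defect is a lenient reference chosen against the authors' own stated judgement, with an endpoint definition that leaves its comparability open.

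**What to change.** 1. In section 3, state that normal imaging without a complication does not count as a grade 3 event, so that the endpoint matches the reasoning behind 12%.
2. In sections 3 and 4, replace 26.3% with 12% as the primary reference.
3. State one decision rule, on the observed count: SDD is flagged as inferior if at least 10 of 45 patients have a grade 3 or higher event (one-sided exact test, alpha 0.05, actual size 0.038). State the alpha.
4. Report 26.7% only as the true rate detectable with 80% power. Used as a cut-off on the observed proportion, in the form of the present rule, it would make 10, 11 and 12 of 45 (22.2% to 26.67%) both inferior and non-inferior.
5. Describe fewer than 10 events as not shown to exceed 12%, and give the exact one-sided 95% upper limit (32% for 9/45). Do not claim non-inferiority.
6. Keep 26.3% as a secondary description, tabulated with the source's broader definition that counts imaging.

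The cost is revised wording in two sections and one recalculated figure. No patients or procedures are added. The price is a stricter rule and a more modest conclusion. A true non-inferiority claim would need more patients: with an illustrative limit of 24%, a true rate of 12% and 80% power, the exact test needs 68 patients at one-sided 0.05, and 45 patients give 54% power.

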### **Research Plan**

#### **1. Study Design**

This is a prospective cohort study evaluating safety, cost and patient satisfaction with SDD for patients undergoing minimally invasive sacrocolpopexy for pelvic organ prolapse. A prospectively collected, historical control group who underwent the same surgical procedure will be utilized to compare these outcomes when applicable. SDD will be facilitated in part by a utilizing novel patient education video created for this study and implementing an ERAS pathway. All patients meeting eligibility criteria will be approached for study participation. Outcomes will be assessed on POD 0/1 and at the routine post-operative follow up visit, generally at 6 weeks after surgery.

**Primary outcomes:** The primary outcome of this study is serious adverse events.

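### The primary safety outcome is judged against two comparators, a fixed 26.3% and the 60-woman POD 1 cohort, with no stated hierarchy, so the same data can be called non-inferior and significantly worse

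*Combined protocol and SAP*

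**What the plan says.** Section 1, Study Design, names one primary outcome: "The primary outcome of this study is serious adverse events". Section 3, Data Collection, defines it by Clavien Dindo grade, "with a grade 3 or higher considered to be a serious adverse event", and gives the decision rule: "we will compare this proportion to the reference proportion of 26.3"%, followed by "A proportion of patients with grade 3 or higher less than 45.1% will be considered non-inferior to the reference". The sample size paragraph of section 4 is built on this one-sample comparison alone, with 45 evaluable patients and 80% power.

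The other comparator is a group of patients. Aim 1 in Specific Aims says: "We will compare incidence of postoperative adverse events between patients undergoing SDD versus a historical control group who were discharged on POD 1". Section 4 repeats the assignment, "We will use data from a historical control group discharged on POD 1 after minimally invasive sacrocolpopexy to examine Aim 1 and Aim 2", describes the group, "This is a cohort of 60 women matching our eligibility criteria from a prospective randomized trial", and adds: "We will utilize this cohort to compare the incidence and severity of procedure-related adverse events and costs between SDD and POD 1". The tests offered for categorical outcomes in section 4 are chi-square or Fisher exact, with significance at P≤0.05, and logistic regression is planned for confounding.

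No section says which comparison is the primary analysis, or what is concluded if the two disagree.

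**The concern.** The study's hypothesis is that SDD is as safe as discharge on POD 1. The plan offers two routes to that conclusion on the same outcome. One tests against a fixed external figure with a wide allowance, and the sample size paragraph itself suspects that figure is too high, preferring about 12%. The other compares with women treated by the same surgeons at the same institutions. If the cohort's rate is well below 26.3%, SDD could be clearly worse than the cohort and still pass the fixed rule.

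Without a stated order, the report can lead with whichever result suits once the data are known. This is the main safety conclusion of a study meant to support wide adoption of SDD.

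**Working it through.** **Inputs.** From the documents: reference 26.3%, cut-off 45.1%, n=45, power 80%, one-sided exact binomial test, cohort of 60, P≤0.05, and 12% as the incidence the authors find more representative. Not in the documents: the cohort's grade 3 or higher rate, and the alpha of the one-sided test (0.05 assumed).

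**1. Reproduce the plan's figure.** With X ~ Bin(45, 0.263), P(X≥17)=0.061 and P(X≥18)=0.031, so the critical count at one-sided 0.05 is 18. Power at 45.1% is P(X≥18 | 0.451)=0.798, and it reaches 80% at 45.15%. The plan's 45.1% is therefore the alternative detectable with 80% power.

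**2. The section 3 rule in counts.** 0.451×45=20.3, so 20/45 (44.4%) or fewer is non-inferior.

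**3. One worked case.** Take 13/45 (28.9%) with SDD and 7/60 (11.7%) in the cohort.
- Fixed rule: 28.9% < 45.1%, so non-inferior. The one-sided exact p against 26.3% is 0.40.
- Cohort: pooled rate 20/105=0.1905. SE=√[0.1905×0.8095×(1/45+1/60)]=0.0774. z=0.1722/0.0774=2.22, so chi-square=4.95 and p=0.026. Fisher p=0.043. SDD is significantly worse.
- Risk difference 17.2 points. Wald 95% CI: 0.1722±1.96×√(0.2889×0.7111/45+0.1167×0.8833/60), which is 1.7 to 32.8 points.

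**4. Range of cohort rates.** The smallest SDD count that is significantly worse than the cohort is shown below. Every count from there to 20/45 is discordant.

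| Cohort | Chi-square from | Fisher from |
|---|---|---|
| 3/60 (5.0%) | 8/45 | 9/45 |
| 7/60 (11.7%) | 12/45 | 13/45 |
| 10/60 (16.7%) | 15/45 | 16/45 |
| 12/60 (20.0%) | 17/45 | 18/45 |
| 14/60 (23.3%) | 19/45 | 20/45 |
| 15/60 (25.0%) | 20/45 | none |
| 16/60 (26.7%) | none | none |

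At 12/45 against 7/60, chi-square gives p=0.048 and Fisher p=0.072, so the choice of test moves the boundary by one patient.

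**5. Chance of a discordant pair.** This sums Bin(45, SDD rate)×Bin(60, cohort rate) over all pairs with at most 20 SDD events and p≤0.05 with SDD worse.

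| True cohort rate | True SDD rate | Chi-square | Fisher |
|---|---|---|---|
| 12% | 12% | 3% | 2% |
| 12% | 18% | 16% | 10% |
| 12% | 24% | 41% | 31% |
| 12% | 26.3% | 51% | 41% |
| 20% | 26.3% | 13% | 9% |

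**6. The cut-off against its own test.** At 18, 19 and 20 of 45 (40.0%, 42.2%, 44.4%) the one-sided exact p against 26.3% is 0.031, 0.015 and 0.006. Section 3 calls all three non-inferior, while the test used for sizing finds each significantly above the reference.

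**The case against.** The best defence is that the hierarchy is implicit. Grade 3 or higher has one explicit rule and one sample size basis, both against 26.3%. The cohort text only says incidence and severity will be compared, covers adverse events broadly, and plans regression adjustment, so an unadjusted chi-square is not its last word. This largely stands: a reader might infer that the plan has no identifiable primary test, and that goes too far. What does not stand is that the label is therefore unnecessary. Aim 1 and the Statistical Plan name the cohort, severity is the Clavien Dindo grade, and the categorical tests cover it.

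A reader might also infer that discordance is the expected result. The documents do not support that. The 12% is the authors' guess for the procedure, not a cohort figure. The 26.3% counted any imaging, even when normal, and a cohort scored that way could sit near it, where the conflict vanishes. The largest probabilities require SDD to at least double the rate.

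Nor is the pair a contradiction in logic. Results can be within a wide allowance of one reference and still differ from another group. Likewise, a count significantly above 26.3% without a significant cohort difference is not a clash between the two comparators as written, because the plan's rule is the 45.1% cut-off. That is the separate defect in step 6.

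**Conclusion.** The point holds as a missing hierarchy with a real consequence: under rules the plan states, one data set can yield a non-inferior safety verdict and a significant excess over the cohort that Aim 1 names. The size is conditional on the unreported cohort rate. The conflict requires that rate to be 15/60 or lower by chi-square, or 14/60 or lower by Fisher. It is rare when SDD is no worse than the cohort and becomes common only when SDD is materially worse, which is when the reading should not be left open. The step 6 result rests on an assumed one-sided alpha of 0.05. This should be fixed before analysis; it does not invalidate the design.

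**What to change.** In sections 1, 3 and 4:

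- Label the one-sample exact comparison with 26.3% as the primary analysis, since n=45 is built on it, and state its one-sided alpha.
- Reconcile the 45.1% cut-off with that test, so that a count significantly above 26.3% cannot also be declared non-inferior.
- Make the cohort comparison of grade 3 or higher events a key secondary, reported as a risk difference with a 95% confidence interval.
- State in advance that if this interval lies wholly above zero (SDD worse), equal safety with POD 1 discharge is reported as not shown, whatever the one-sample result.

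The last rule can only withhold the claim and cannot create it, and it defines disagreement exactly. In the worked case (1.7 to 32.8 points) it would withhold the claim. It matters because the primary reference is one the authors suspect is too high.

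The cost is a few sentences, with no extra patients or data. The sponsor gives up choosing the comparator after seeing the results, and accepts a small chance (about 3% by chi-square if both rates are 12%) of withholding the claim when the rates are equal.
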